6. ETHICS

GBS2 will be conducted according to the principles of the International Conference on Harmonisation of Technical Requirements for Registration of Pharmaceuticals for Human Use, and Good Clinical Practice Guidelines.

All centres will be required to sign an Investigator's Agreement, detailing their commitment to strategy implementation, accrual, compliance, Good Clinical Practice, confidentiality and publication. Deviations from the agreement will be monitored and the Trial Steering Committee (TSC) will decide whether any action needs to be taken, e.g. withdrawal of funding, or suspension of the centre.

The Trial Office will ensure researchers not employed by an NHS organisation hold an NHS research passport that includes the maternity units in their region.

Regulatory and Ethical Approval

Ethical and Trust Management Approval

The GBS2 study has a favourable ethical opinion from the West Midlands - Edgbaston Multi-centre Research Ethics Committee (MREC) approval Ref: 16/WM/0036, confirming that the study design respects the rights, safety and wellbeing of the participants.

The Comprehensive Research Network and NHS Trust R&D managers will conduct governance checks and assess the facilities and resources needed to run the GBS2 study in order to grant host site permission to start collecting data. The Trial Office in Birmingham is able to help the local Principal Investigator in the process of the site specific assessment by completing as much of Site Specific Information section of the standard IRAS form as possible. The local Principal Investigator will be responsible for liaison with the Trust management with respect to locality issues and obtaining the necessary signatures at their Trust.

After Trust approval has been obtained, the Trial Office will arrange for the maternity unit to be randomised to either a standard risk factor, or rapid test based screening strategy and this will be conveyed to the local Principal Investigator. A start date and duration for the study period will then be agreed.

Funding and Cost implications

The research costs of the trial are funded by a grant from the National Institute of Health Research Health Technology Assessment Programme awarded to Queen Mary College, University of London.

The GBS2 study will have minimal extra 'service support' costs for participating hospitals, due to the no-consent model of trial recruitment. Excess treatment costs associated with the rapid tests have been estimated from the quotations received from Cepheid and the ability of the Trust's to underwrite these costs will be discussed prior to randomisation, on the understanding that there will be a 50% chance of the Trust being called upon to fund such costs. On top of this Trusts assigned the rapid test will find that there are hidden savings. These include:

- reducing antibiotic use by better identifying and only targeting those women colonised with GBS, Intrapartum antibiotics will only be given where they are needed
- reducing the time spent in hospital by knowing the GBS colonisation status of the mother with considerable certainty, babies born to mothers with risk factors for, but who are not colonised with GBS can be discharged home sooner and with less medical intervention

reducing readmissions – Should a baby be born to a mother who has tested
positive for GBS colonisation then this will aid clinical staff in judging if the
mother has received sufficient Intrapartum antibiotics to prevent vertical
transmission of GBS to her baby. By taking any necessary action earlier, the
need to readmit at a later date will be reduced

The costs of the swabs and transport tube and the microbiology culture for GBS are research costs and will be reimbursed pro-rata from the research grant.

Indemnity

Queen Mary, University of London will act as a Sponsor, as defined by the Research Governance Framework for Health and Social Care (April 2005) for the project. The project will also be covered by the sponsor's insurance brokers on a "No Faults Compensation for Clinical Trials and/or Human Volunteer Studies". This policy will indemnify/cover the insured in respect of their legal liabilities arising out of the insured's activities.

Publication

A meeting will be held after the end of the study to allow discussion of the main results among the collaborators prior to publication. The success of the study depends entirely on the wholehearted collaboration of a large number of doctors, nurses and others. For this reason, chief credit for the main results will be given not to the committees or central organisers but to all those who have collaborated in the study. Centres wishing to publish local data obtained from participants in the GBS2 Trial should submit a request outlining their audit or research project to the GBS2 TSC who will give any request due consideration.

7. SAFETY CONSIDERATIONS:

There are no safety concerns above those associated with standard care for any participants in the GBS2 trial. It goes without saying that the clinical staff must take any measures they see fit at any time to ensure the safety and protection of the clinical trial subjects from any immediate hazard to their health or safety. In this instance, the approval of the REC prior to implementing these safety measures is not required.

Should such an intervention be necessary it is the responsibility of the local PI to inform the co-ordinating unit in writing within 3 days of any such intervention taking place. The sponsor (care of the Joint Research Management Office) must be sent a copy of the correspondence with regards to this matter by the co-ordinating unit.

8. DATA HANDLING AND RECORD KEEPING:

Electronic data transfer and paper data collection forms

The National Maternity Information System database and / or the dedicated data collection sheets will be the source for routinely recorded demographic and delivery data. Data will be collected in batches using the mother's unique trial number as anonymous linkers. Where data is requested from the National Maternity Information System each individual's unique trial number will be returned to the site accompanied by a request to download this woman's data from the Trust's electronic systems, anonymise this, then securely return these data to the Main Trial office. Antibiotic prescription data will be extracted from either maternal prescription charts or pharmacy records for the labour ward, which will be cross-referenced with data already collected using the unique trial number. The GBS2 Trial Office will work with the unit's information systems managers in obtaining these data. The availability of, and access to, electronic data will be negotiated with each unit's information systems manager and agreed during the local research governance approval process.

Most maternity units do not collect data such as risk factors electronically, so some paper data collection forms will be required. The GBS2 checklist described above will collate all this information and be linked by the woman's and her baby's unique trial number.

Information on the rapid tests will be downloaded from the computer attached to the GeneXpert machine at intervals throughout the study period and securely transferred using secure socket layer (SSL) encryption technology to the GBS2 Trials Office. Depending on the local site this transfer will either take place via a secure electronic transfer. If local conditions do not allow this then local Trust staff will download the data onto a suitably encrypted and locked USB device which will be securely transported to the trials office.

[figure not shown]
Confidentiality of personal data

Electronic data retrieved from Trusts and from the GeneXpert machine will not contain any identifiers such as names or address, but will require the use of a unique linker such as the unique trial number. As the results from the rapid test machine will be used to direct patient care, Good Clinical Practice demands that a copy of the results are lodged in the patients notes. To maintain confidentiality but still ensure that trial data is collected the machine will produce two print-outs stating the result of the test. The first will contain a number of identifiers plus the result of the test. This print out will be placed in the patient's notes by a member of the staff responsible for the woman's care and the result acted on appropriately. The second print out will be produced which just displays the woman's unique trial number and various anonymous parameters such as the time the test started, the time the test completed, if the test failed the reason why, and the colonisation status of the mother. The results displayed on this print out will be uploaded onto the trials system by a local member of staff responsible for the care of the woman or the trial research midwife. This print out will be placed with the paper trial records which will be stored securely at the local site.

Once transferred to the GBS2 Study Office, data will be stored in a master database and linked using the unique trial number. This system also provides an effective archive which will allow results to be traced by the participating Trust should any queries arrive or if they are required in the future e.g. to answer the threat of any legal action.

The dataflow pathway for this is shown in Figure 3 (below)

Version 1.0 22nd December 2015 GBS2 Page 51 of 81

As noted, data collected on paper, for example the GBS checklist, will be entered onto a secure computer database. Paper derived records will be entered directly by the local site *via* the internet using secure socket layer (SSL) encryption technology. Built in access controls will ensure that local trials staff will only be able to view anonymised patient information derived from their site, and will prevent disclosure of rapid test results to the person entering microbiological data on to the database.

Results derived from participants in the sub-study examining the relatedness of any bacterial transmission between the mother and her infant after its birth will be stored against their trial number on a secure, independent database system at a site separate to that where the information on the main (cluster) trial is held. Patient identifiable information will not be available to any members of the trial team.

Specimen identification, processing and storage

The specimens collected will depend upon the location of the trial centre. In centres in Birmingham and the West Midlands who are assigned a rapid test, specimens will be collected from the woman presenting to the labour ward and her neonate.

Women attending units using the rapid test, and who are identified as having factors associated with GBS colonisation will be asked to provide a swab of their vaginal – and rectal mucosa using a multi-headed swab. One of these swab heads will be sent to the local microbiology department using the local test request procedure. The other swab head will be applied to the Cepheid GeneXpert rapid test cartridge.

Neonates born to women who have risk factors associated with GBS colonisation in centres assigned a rapid test kit will have a swab taken from their ear canal at the earliest possible opportunity after birth. This will be sent to the local microbiology lab where it will undergo selective enrichment. The presence of any GBS will be recorded.

In centres in London and the South-East assigned a rapid test kit, women with risk factors associated with GBS colonization, will be swabbed with a triple headed swab. After exposure, as in centres in the West Midlands, the first swab will be applied to a rapid test cartridge, whilst the second swab will be sent to microbiology where it will undergo a culture process suitable to detect the presence of GBS. In centres in London and the South-East who have a rapid test system the third swab head will be being sent to the microbiology department at Bart's Health NHS Trust labelled only with the woman's trial number.

The third maternal swab will be held for a period of up to 96 hours for written, informed consent to be granted. Once the midwifery staff inform the sub-study Research Assistant that written informed consent has been granted this will be passed to the microbiology department who will commence microbiological culture on Swab 3.

If consent is not granted then the third swab will be disposed of in a safe and secure manner.

At five weeks post-delivery the sub-study trial office will request that the local midwifery team send out a follow-up sample collection pack consisting of a faecal sample pot accompanied by a covering letter and a suitable prepaid, addressed transport container to the woman's home address. The woman will be asked to take a sample of her baby's expelled faecal material, place it in the pot and return it in the prepaid transport container provided. The unique trial number displayed on the pot will allow the lab to identify the infant's sample and link it to that of the mother. Should this sample of the baby's faecal material not be forthcoming after the first request then one repeat and final request will be sent to the mother at nine weeks after her baby is born. If no faecal sample has been returned by twelve weeks after the sub-study trial office has logged notification of consent being received then the sample will be marked as 'not expected' and no further follow-up attempts will be made.

Good laboratory practice demands that any swabs sent for clinical microbiology are accompanied by at least two unique identifiers to ensure that the results are recorded in the correct set of notes. Any swab not accompanied by these identifiers are simply disposed of without processing. To ensure that the GBS2 swabs are processed, all clinical microbiology requested on Swabs 2 (the mother's vaginal / rectal swab) and Swab 4 (the neonatal ear swab) will follow the established local procedure for requesting and reporting microbiological tests. The request form or bag will be flagged with a GBS2 sticker to alert the microbiology department to follow the culture protocol and reporting arrangements.

The other maternal vaginal-rectal swab (Swab 1) will be used immediately to inoculate the test cartridge for the rapid point of care test for GBS and will not need to be labelled.

Swabs sent to microbiology lab for the determination of the GBS colonisation status will be introduced into Todd Hewitt broth for overnight enrichment at 37°C. This enriched broth will be subcultured onto chromogenic GBS agar plates where it will undergo a second overnight aerobic incubation at 37°C. GBS will be identified by the presence of pink-red colonies on this chromogenic media.

Results of the microbiological culture will need to be recorded in the patients' notes according to local practice, mindful that these results will not be available until after delivery of the baby. Microbiological data will need to be transferred to the trial database by either a member of the microbiology department, a local research nurse or if possible, by direct data transfer from the sites' information management system. Where manual data entry is required, the data entry screen will not allow review of the rapid test results for that patient by those outside of the study office, thus reducing the risk of review bias. All data transfers, no matter how they are performed will use only the unique trial number as a linker. No identifiable data will be available to the trial team.

Upon notification from the local midwife that written consent has been acquired the third vaginal / rectal swab obtained from the mother during labour, or the faecal sample obtained from the infant after it is born will be exposed to a range of selective and non-selective culture methods suitable to detect the presence of any GBS, MRSA, VRE or Es β L-producing Enterobacteriaceae. Any antibiotic resistant isolates of these bacteria will be stored for subsequent molecular characterisation.

Record Retention

Archiving will be undertaken by the Sponsor following submission of the end of trial report to the funding body. GBS2 is not a clinical trial of an investigational medicinal product so no minimum retention periods are specified. The trial dataset (which is anonymised) will be put into a form allowing the computer database to be legacy archived indefinitely.

Since GBS2 is sponsored by Queen Mary (University of London), the approved repository for long-term storage of local records is the Barts Trust Modern Records Centre where paper records will be kept for a minimum of twenty years.

Principal Investigators are responsible for the secure archiving of essential trial documents for their site according to the local policy.

No personal identifiable information on the woman and her offspring participating in the sub-study will be available to the trial team. The local midwifery staff will inform the sub-study Research Assistant of the woman's trial number once written consent has been obtained. This trial number will be used to link the data collected and no information which can be used to identify the woman or her child will be passed to any member of the trial team.

9. LABORATORIES (if applicable)

Central/Local Laboratories

In centres randomised to receive a rapid test system, the participating trust's microbiology laboratory will be requested to culture any bacteria adhering to the mother's vaginal / rectal swab, and that taken from the neonate's ear canal on a selective media, and to report on the presence or absence of GBS.

Lab Procedures

Women attending units using the rapid test, and who are identified as having factors associated with GBS colonisation will be asked to provide a vaginal / rectal swab using a multi-headed swab. One of the swab heads will be sent to the local microbiology laboratory for GBS culture using the established local systems for requesting microbiological tests. The request form or bag will be flagged with a GBS2 sticker to alert the microbiology department to follow the culture protocol and

reporting arrangements. The other vaginal – rectal swab will be used in the rapid point of care test for GBS and will not need to be labelled.

As soon as is convenient after its birth, a swab will be gently rotated in the neonate's ear canal. This swab will be placed in a transport tube and sent to the local microbiology laboratory for GBS culture using established local systems for requesting microbiological tests. The request form or bag will be flagged with a GBS2 sticker to alert the microbiology department to follow the culture protocol and reporting arrangements. The neonatal ear swab will not be applied to the rapid test system.

Upon receipt in Microbiology the mother's rectal-vaginal swab and that taken from the neonate's ear canal will be introduced into a Todd Hewitt broth for overnight enrichment at 37°C. This enriched broth will be sub-cultured onto chromogenic GBS agar plates where it will undergo a second overnight aerobic incubation at 37°C. GBS will be identified by the presence of pink-red colonies on this chromogenic media.

The sub-study determining the degree of relatedness between certain bacteria colonising the vaginal tract and lower gut of the mother and the lower gut of her baby at six weeks of age will only take place in centres in London and the South-East which are assigned a rapid test machine. In these centres, women joining the relatedness sub-study examining the source of new born colonisation by three types of bacteria will give written, informed consent for their child to be to be followed-up. Should a woman decline to provide consent, or if 96 hours have passed since the receipt of the third swab in Bart's and the London's Microbiology Department, then this third swab will not be processed but disposed of in a suitable manner compliant with local policies.

Upon notification from the local midwife that written consent has been obtained from the participant this third swab vaginal / rectal swab will be exposed to a range of selective and non-selective culture methods suitable to detect the presence of any GBS, MRSA, VRE or EsβL-producing Enterobacteriaceae. Any bacteria of interest will be profiled using a variety of methods, including matrix-assisted laser desorption ionization—time of flight mass spectrometry, an antibiotic susceptibility profile will be undertaken, and genetic analyses (including analysis of resistance mechanisms). No personal identifiable information will be available to either the sub-study Research Assistant or microbiology staff.

Once a period of five weeks has elapsed from when the trial office was notified that consent had been given the sub-study Research Assistant will supply the maternity unit with a faecal sample pot labelled with a unique number. The sub-study trial Research Assistant will record the number on the pot alongside the mother's trial number.

After checking with the Community Midwifery team that nothing untoward has happened to the child then maternity unit staff will send out a follow-up sample collection pack. This pack will consist of a faecal sample pot accompanied by a covering letter and a suitable prepaid, addressed transport container to the woman's home address requesting a sample of her child's expelled faecal material be collected from its nappy.

Following receipt of this faecal sample the Microbiology Laboratory at Barts Health NHS trust will inform the sub-study Research Assistant who will record this against the woman's unique trial number. If this sample is not marked as received then at nine weeks after notification the sub-study trial co-ordinator will request that the mother is sent another follow-up sample collection pack. Should this fail to be returned by twelve weeks after notification of the receipt of consent then the sample will be marked as 'not received' and no further attempts to obtain a faecal sample will be made.

The pot will be placed in a suitable transport container and returned to the central microbiology lab at Barts Health NHS Trust. The post room at Pathology and Pharmacy Building will sort through all deliveries and any samples labelled for the GBS2 sub study will be directed to the appropriate lab for analysis

Upon receipt the number on the pot will be recorded and the sub-study trial coordinator notified. The bacterial flora present in the gut bacteria colonising the infant's faeces will be compared with that obtained from the vaginal – rectal swab taken from the mother in labour.

Data Preparation and Collection

Results of the microbiological culture for the presence of GBS on Swab 2 (Mother's vaginal / rectal) and Swab 4 (Baby's ear canal swab) will need to be recorded in the patients' notes according to local practice. Results will need to be transferred to the trial database by either a member of the microbiology department, a local research nurse or if possible, by direct data transfer from the sites' information management system. Where manual data entry is required, the data entry screen will not allow review of the rapid test results for that patient, thus reducing the risk of review bias.

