The purpose of the obtaining the baseline current IAP usage rates is to stratify the randomisation of clusters. With a relatively small number of clusters it may be inappropriate to attempt to pair clusters. As clusters will be randomised in up to four waves, it is more appropriate to stratify the randomisation of clusters within each wave by baseline IAP rate. Maternity units will be randomised to follow either the risk factor based screening strategy or the rapid test strategy to direct the decision to offer IAP.

Version 1.0 22nd December 2015 GBS2 Page 31 of 81

Risk based screening units (i.e. those not assigned a rapid test system)

All women considered eligible for the study according to the risk factors for GBS transmission described should be offered IAP.

If a woman is pyrexic, or suspected or confirmed to have chorioamniotis, broad spectrum antibiotics (e.g. fourth generation cephalosporins) should be given immediately.

The use of IAP will be collected, including information of whether IAP was declined or deemed too late given the progression of the labour, along with the date and time the IAP was initiated.

Rapid test screening units

Supply of trial consumables

Units randomised to receive the rapid point of care test will be supplied with a Cepheid GeneXpert GBS rapid testing system plus a sufficient number of GeneXpert GBS test cartridges and other consumables to cover the number of women projected to have GBS risk factors presenting to their unit during the study period. Should stocks of consumables or test cartridges start to run low (to a level of around 25% of that initially supplied) then the centre should contact the Trials Office in Birmingham who will arrange re-supply.

Obtaining a vaginal-rectal swab

The use of the rapid test for screening will be restricted to women who present to the labour ward and who exhibit at least one of the risk factors associated with GBS colonisation.

Depending on the stage of labour the swabs will be obtained by either the woman herself, or a suitably qualified, trained, and locally approved member of the woman's care team. This could be on admission to the labour ward, before a vaginal examination is performed, or after a risk factor is detected - for example, maternal fever is observed.

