A sample size of 676 would provide 90% chance of us accruing enough GBS colonised women to have 90% power to show the sensitivity of the GBS test to be statistically significantly (with p<0.05) greater than 90% should the meta-analytical estimate of its performance (96.4%) be correct whilst allowing for 10% loss from failed tests, based on the GBS prevalence observed in GBS1, which was 29.8% (89/299, 95% CI: 24.6%-35.2%). Of the 606 participants with data we would expect 167 to be GBS carriers and 439 to be negative for GBS colonisation. If the prevalence of GBS colonisation is actually at the lower 95% confidence interval from GBS1, namely 24.6%, then 673 total women will give 90% chance of observing 136 cases of GBS colonisation, including 10% lost tests.

The 95% Cis we would observe on sensitivities and specificities of 85%, 90%, 95% and 98% with a sample size of 676 (606 with data) are shown in **Table 1** and have adequate precision (sensitivity within 10%, specificity within 6%) for modelling.

Point estimate	CI for sensitivity (n = 167)	CI for specificity ($n = 439$)
85	78.7 – 90.1	81.3 – 88.2
90	84.2 – 94.0	86.8 – 92.7
95	90.9 – 97.9	92.5 – 96.8
98	94.8 – 99.6	96.2 – 99.1

Table 1: Confidence Intervals for sensitivity and specificity at various point estimates Cluster

randomised trial

The focus of this sample size calculation is on the effectiveness of the rapid GBS test within a cluster randomised trial (CRT) in which the number of clusters, in this case maternity units, is limited by the by the willingness of NHS Trusts to participate, but the number of potential participants is only limited by the duration of study period.

The CRT requires a minimum of 8 maternity units per screening strategy i.e. a total 16 units. Based on assumptions cited below, we estimate that the sample size per cluster will be approximately 83. This equates to a total sample size of approximately 664 participants per arm, and so therefore allows sufficient numbers of women to be recruited for the test accuracy study too.

As there are two arms (Standard Practice / Rapid Test), each of at least 664 participants this gives a projected sample size of 1,328 women. This has been rounded up to a target sample size of 1,340 women.

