We have not acknowledged varying cluster sizes in our calculations, as we consider the coefficient of variation of unit delivery sizes to be small (approximately 0.21 based on annual delivery rates for 2013) and can be altered by varying the study duration at maternity units. Given our conservative assumptions, and that the impact of the rapid test on the rate of IAP provided is expected to be large, it is expected that the impact of any varying cluster sizes will be minimal.

Analysis methods

Test accuracy study

The accuracy of the rapid test for detection of GBS colonisation will be expressed as sensitivity, specificity, positive and negative predictive values, and positive and negative likelihood ratios, along with their associated 95% confidence intervals.

Cluster randomised trial

The baseline characteristics, for example parity, ethnicity, risk factors and gestational age at onset of labour will be summarised as means and standard deviations, or medians and inter-quartile ranges, grouped by unit allocation (risk factor based screening or rapid test based screening).

Analyses of outcomes will be by intention to treat. As randomisation will be at the maternity unit level, appropriate statistical methods to account for the clustering within units will be used in the analysis.

The primary aim of the study is to evaluate whether the proportion of women prescribed IAP for prevention of GBS transmission differs between the screening strategy groups. In statistical terms the null-hypothesis, that of no difference can be tested using a mixed logistic regression model with prescription of IAP as the dependent variable, study screening strategy group as the independent variable, and maternity unit as a grouping (random effect) variable. These models will be fitted using population averaged models (similar to multilevel models) using GEE methods in STATA. Population averaged models, as opposed to random effects models, will be used as within the framework of cluster randomised trials: random effects models both lack appropriate interpretation and might be biased.[52] Similar models will be fitted for secondary outcomes and appropriate link functions used for outcomes which are not binary.

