A conservative estimate of the number of eligible deliveries per 4 weeks in the participating Trusts indicates an average of 71 deliveries per site, so a study period of 4-5 weeks would be sufficient at all sites. We consider this period the minimum needed should a Trust be assigned a rapid test to implement its use as policy.

Economic analysis

Resource use data will be collected within GBS2 to estimate the costs associated with the diagnosis of women using the rapid test compared to risk factor alone based screening. The main resources to be monitored include:

- The resources required to perform the GeneXpert rapid test and act on its results
- Any resource use associated with identifying risk factors, and establishing they exist before acting on the result
- The administration of IAP and associated resource use (midwife time, monitoring patient)
- Monitoring, investigation and management of infants born to women exhibiting risk factors for GBS transmission
- Any extended stays on post-natal ward for neonatal monitoring and any admissions to neonatal unit (special, high or intensive care)

Estimates of the incidence of EOGBS disease, treatment effects of maternal antibiotics on EOGBS disease, and mortality rates will be based on secondary sources.[54]

Information on unit costs or prices will be obtained and assigned to each resource item in order that an overall cost per patient can be calculated. Cost data will be collected from two principle sources:

Firstly, the test accuracy study will provide resource use data to estimate costs incurred in administering the rapid test. Where possible cost data, such as cost of midwife time etc will be collected from routine sources, including those obtained from Curtis and Netten[55] and hospital finance departments. Many cost sources are already identified and available in recently published sources including a systematic

review and the GBS1 study.[56] These cost data will be appropriately updated by revisiting the relevant sources.

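### Each unit's start date and duration are agreed after its allocation is disclosed, so the inclusion window can be influenced by knowledge of the arm

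*Protocol*

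**What the plan says.** Section 6 (Ethical and Trust Management Approval) gives the sequence. After Trust approval the Trial Office arranges randomisation of the unit to the risk-factor or the "rapid test based screening strategy and this will be conveyed to the local Principal Investigator". The next sentence reads "A start date and duration for the study period will then be agreed".

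The length of the window is not fixed elsewhere. Under Statistical considerations, the cluster trial text says that the size of a cluster is limited only by how long the unit runs, and that variation in delivery numbers "can be altered by varying the study duration at maternity units". Accrual and study initiation roll-out gives an expectation, "so a study period of 4-5 weeks would be sufficient at all sites", and adds "We consider this period the minimum needed should a Trust be assigned a rapid test to implement its use as policy".

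Two provisions bear on calendar balance. Accrual and study initiation roll-out plans to open the two arms in equal numbers, wave by wave. Section 5 (Randomisation of maternity units) says "it is more appropriate to stratify the randomisation of clusters within each wave by baseline IAP rate".

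The protocol does not require a unit's dates to be set before allocation, or the two arms to close by the same rule.

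**The concern.** Section 5 (No consent model) accepts the principle that participants in a cluster trial should be identified before their cluster is randomised. It explains that risk factors arising in labour make this impossible, and relies instead on including every woman with a risk factor, without individual research consent. That is a sound answer to selection by midwife or by refusal. It works fully only if the period that defines every woman is itself chosen without knowledge of the arm. Here that period is agreed with someone who knows the arm.

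The protocol gives ordinary, innocent reasons why timing could differ by arm. Rapid-test units must have a machine and cartridges in place, whereas the trial packs at control units hold only data forms. The stated minimum duration is also explained by what a unit needs if it is allocated the test. The primary outcome is a prescribing process measure, which may vary with period and staffing, and the primary analysis is unadjusted. A systematic difference in timing between arms would therefore pass into the main comparison.

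**Working it through.** **Sequence.** Section 6 gives the order as approval, randomisation, allocation conveyed, window agreed. Nothing in section 5 or under Statistical considerations reverses it or fixes dates earlier. This step needs no arithmetic.

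**Length of the window.** There are two inputs from the protocol. The eligible-delivery estimate per four weeks "indicates an average of 71 deliveries per site", and for cluster size "we estimate that the sample size per cluster will be approximately 83".

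- Weeks needed = 83 / 71 x 4 = 4.68. The protocol's 4-5 weeks is reproduced.
- Per arm: 8 units x 83 = 664. Total: 2 x 664 = 1,328, as stated.
- Women per unit by duration, at 71/4 = 17.75 per week: 71 in 4 weeks, about 89 in 5, about 107 in 6, 142 in 8.

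Duration thus directly determines how many women enter and which ones. A shift of five weeks exceeds 4.68 weeks, so the old and new windows share no women.

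**Do balanced waves make the windows coincide?** Site support is spread over 12 months, with up to four waves. Assuming four equal waves, each spans 12/4 = 3 months, about 13 weeks, which is 13/4.68 = 2.8 window lengths. Two units in the same wave could therefore have windows that do not overlap. The wave limits the gap between arms but does not remove it.

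**Is this a power problem?** With effective sample size per arm = 8 x 83 / (1 + 82 x ICC):

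- ICC 0.2: 664/17.4 = 38.2. ICC 0.01: 664/1.82 = 364.8.
- For the four Table 2 scenarios with a 75% control rate, power is 92-94% by the normal approximation and about 90-91% with a t test on 14 degrees of freedom. This agrees with the stated 90%.
- With unequal windows, assumed at 71 women per control unit and 142 per rapid-test unit, power is 92-95% by the normal approximation.

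Power is hardly affected. The issue is comparability of the arms.

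**The case against.** The strongest reply is that the plan already contains the relevant safeguards. The arms open in equal numbers in each wave, randomisation is stratified within wave, and a single expected duration of 4-5 weeks is given for all sites. The flexibility in duration is mentioned in order to even out cluster sizes when units differ in delivery volume (coefficient of variation about 0.21), which has nothing to do with allocation. Within the window all women are screened, so the usual post-allocation selection step is absent. The date is agreed after the Trial Office has arranged randomisation, and nothing says that a unit chooses it alone. Changing which women are in the window is not in itself bias.

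All of this stands and makes the point smaller. It does not answer it, because no safeguard fixes a given unit's dates or closing rule before its arm is known.

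A reader might go further and infer that the order breaks the concurrent comparison within waves. The documents show that windows can differ by arm, not that they will. A reader might also infer that allocations are predictable, since few units fall in each wave and stratum. That would need units randomised one at a time, a particular number of strata and forced balance within each stratum. The protocol states none of these, and its reference to randomising clusters in waves reads at least as naturally as randomising a wave together.

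**Conclusion.** The point holds as a matter of procedure. The protocol affirmatively places agreement of the study window after disclosure of the allocation, in a no-consent trial where that window is the main remaining control over which eligible women are included. Wave balance and the common 4-5 week expectation reduce the exposure without closing it.

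No size can be put on the bias. A reader might infer a few percentage points by supposing a monthly drift in prescribing and a lag between arms, but the documents give neither figure. Nor is there a single yardstick to set it against: with a 75% control rate, Table 2's detectable difference runs from 75 - 63 = 12 points at an ICC of 0.01 to 75 - 38 = 37 points at 0.2. The conclusion rests on the stated sequence and on the 4.7-week window, not on an assumed effect. It is a worthwhile, low-cost improvement rather than a flaw that undermines the trial.

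**What to change.** Amend section 6 (Ethical and Trust Management Approval) so that, before a unit's allocation is disclosed, the Trial Office records:

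- the planned start date, allowing the same set-up period whichever arm is allocated;
- the closing rule, either a set number of weeks or a set number of eligible women, the same in both arms, with any adjustment for the unit's delivery volume fixed at that time.

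Bring the sentences on varying duration and on the 4-5 week period into line with this rule. Report actual start and end dates by arm, with reasons for departures from plan.

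This changes wording and trial-office procedure, not sample size or analysis. The downside is that some control units wait through a set-up period they do not need, which adds some delay within the 12-month roll-out.
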